### 5.3 Exploratory Endpoints

- Exploratory endpoints will be defined in the Statistical Analysis Plan (SAP).

	No.: CP 65007	REV. C
	TITLE: Disrupt PAD BTK II Study	
	CLASS: CLINICAL PROTOCOL	PAGE 21 OF 71

## 6.0 STUDY DESIGN

---

The Disrupt PAD BTK II study is a post-market, prospective, multi-center, single-arm study of the Shockwave Peripheral IVL System to treat calcified peripheral arteries. There is no control arm as all Peripheral IVL catheters evaluated in this clinical study have received market approval. Adjunctive therapy usage is limited to minimize bias in regard to study results. Use of adjunctive therapy like cutting/scoring balloons, re-entry or atherectomy devices in target lesions is therefore not allowed.

### 6.1 Regulatory Status

Per ISO 14155:2020, the PAD BTK II study is a post-market clinical investigation defined as a study carried out following market approval of a medical device, intended to answer specific questions relating to effectiveness or safety of a medical device when used in accordance with its approved labeling.

### 6.2 Clinical Development Stage

Per ISO 14155:2020, the medical devices being used in the PAD BTK II study are in the post-market stage which includes additional confirmatory clinical investigations to establish effectiveness of the medical device in a broader population of users and subjects in comparison to previous studies. Also included are observational clinical investigations for better understanding of device safety, such as rare adverse events and long-term outcomes.

### 6.3 Type of Clinical Investigation Design

Per ISO 14155:2020, the PAD BTK II study is considered to be an observational clinical investigation defined as a study that draws inferences about the possible effect of an intervention on subjects, but does not require the investigator to assign subjects into intervention groups or to collect data variables beyond those available throughout the course of normal clinical practice and burden to the subject. See Sections 7.6 through 7.8 for information on data collection requirements and assessment of burden to the subject.

### 6.4 Description of Clinical Investigation

Per ISO 14155:2020, the PAD BTK II study is considered to be a post-market clinical investigation as it is intended to answer specific questions relating to effectiveness or safety of a medical device when used in accordance with its approved labelling.

### 6.5 Burden to Subjects

Per ISO 14155:2020, the PAD BTK II study is considered to be a non-interventional clinical investigation. No additional invasive or burdensome diagnostic or monitoring procedures are applied to the subjects and epidemiological methods are used for the analysis of collected data.

	No.: CP 65007	REV. C
	TITLE: Disrupt PAD BTK II Study	
	CLASS: CLINICAL PROTOCOL	PAGE 22 OF 71

Subjects are not assigned to an intervention group and the majority of data collection requirements fall within the course of normal clinical practice including physical exam, ABI/TBI, Rutherford Category assessment, and duplex ultrasound. The VascuQol questionnaire may not be standard of care at all centers; however, the assessment is non-invasive, introduces no additional risk, and is not considered to be an additional burden to the subject.

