## 6.9 IVUS Sub-study

Up to 50 subjects will be enrolled in an optional IVUS Sub-study. All study centers with intravascular ultrasound (IVUS) imaging capability will have the opportunity to participate in the Sub-study. A separate IVUS protocol will be provided to participating study centers.

	No.: CP 65007	REV. C
	TITLE: Disrupt PAD BTK II Study	
	CLASS: CLINICAL PROTOCOL	PAGE 23 OF 71

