**Table 1. Schedule of Events and Evaluations**

Assessment	Screening / Baseline	Enrollment and Procedure	Discharge 	30 Days (±7 days)	6 Months (180±30 days)	12 Months (365±30 days)	24 Months (730±30 days)	TLR
Eligibility	✓							
Informed Consent 	✓							
Medical History	✓							
Physical Exam	✓			✓	✓	✓	✓	
Baseline Labs (eGFR)	✓							

	No.: CP 65007	REV. C
	TITLE: Disrupt PAD BTK II Study	
	CLASS: CLINICAL PROTOCOL	

Assessment	Screening / Baseline	Enrollment and Procedure	Discharge 	30 Days (±7 days)	6 Months (180±30 days)	12 Months (365±30 days)	24 Months (730±30 days)	TLR
Pregnancy Test	✓							
Ankle-Brachial Index/Toe-Brachial Index (ABI/TBI)	✓ 			✓	✓	✓	✓	
Rutherford Category (RC)	✓			✓	✓	✓	✓	
VascuQoL-6 Questionnaire	✓			✓	✓	✓	✓	
Wound Healing Assessment (including photographs)	✓ 			✓	✓	✓	✓	
Medications (anticoagulants & antiplatelets)	✓	✓	✓	✓	✓	✓	✓	
Angiogram		✓						✓ 
IVUS (sub-study)		✓ 						
Duplex Ultrasound (DUS)					✓ 	✓ 		

	No.: CP 65007	REV. C
	TITLE: Disrupt PAD BTK II Study	
	CLASS: CLINICAL PROTOCOL	

Assessment	Screening / Baseline	Enrollment and Procedure	Discharge 	30 Days (±7 days)	6 Months (180±30 days)	12 Months (365±30 days)	24 Months (730±30 days)	TLR
Adverse Events		✓	✓	✓	✓	✓	✓	✓

TLR = target lesion revascularization; DUS = duplex ultrasound; ABI = ankle-brachial index; TBI = toe-brachial index; QoL = quality of life

1. Consent to be obtained within 30 days prior to procedure.
2. Within 60 days prior to procedure.
3. For the IVUS Sub-study, IVUS imaging is required at baseline, immediately post-IVL, and end of procedure.
4. Within 12-24 hours post procedure or prior to hospital discharge, whichever occurs first.
5. Angiographic images acquired as standard of care prior to the TLR should be submitted to the core lab.
6. Within 45 days of procedure.
7. In the event of a non-diagnostic DUS, a 90-day extension is allowed on the upper limit of the window for the 6- and 12-month visits.

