#### **7.7.5 Definition of Enrollment**

The definition of enrollment is when the subject signs informed consent, meets all general & angiographic eligibility criteria, and the IVL catheter has been inserted over a 0.014" guidewire (which had been previously passed across the target lesion).

	No.: CP 65007	REV. C
	TITLE: Disrupt PAD BTK II Study	
	CLASS: CLINICAL PROTOCOL	PAGE 32 OF 71

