### 8.3 Risks Associated with Participation in the Clinical Investigation

All assessments (with the exception of questionnaires) are considered to be standard of care, but may be conducted more frequently to comply with the follow-up visit schedule. Non-invasive testing includes physical exams, ABI/TBI, Rutherford Category assessments, wound healing assessments, and duplex ultrasounds. All of this testing poses minimal risk to the subject. The VascuQol questionnaire may not be standard of care at all centers; however, the assessment is non-invasive, introduces no additional risk, and is not considered to be an additional burden to the subject. For procedure-related risks, please refer to the current IFUs.

A risk management plan was established to outline the study-specific approach that will be implemented to focus on specific risks and area(s) of greatest need, which are considered to have the most potential to impact subject safety and data quality.

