## 10.4 Serious and Non-serious Adverse Event Reporting Requirements

### 10.4.1 AE Reporting Requirements

All AE information will be collected from enrollment through 24 months follow-up. Reporting will be carried out in accordance with national regulations. Site personnel will enter all AEs into an AE eCRF in EDC. AEs should be reported in the subject's medical records as applicable and on the Adverse Event Case Report Form (AE CRF). Data reported should include date of onset, treatment, resolution, and an assessment of both seriousness and relationship to the study device and procedure. AEs will be followed until the event has resolved (in the case of permanent impairment, the event will be followed until it stabilizes, and the overall clinical outcome has been ascertained).

Any AEs that meet IRB/EC reporting requirements must be reported per the institution's policy.

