### 11.2 Informed Consent

The Investigator is responsible for ensuring that all applicable local, national, Declaration of Helsinki, EU MDR 2017/745, and ISO 14155:2020 requirements in the clinical study are met when completing the informed consent process. It is the responsibility of the Investigator to ensure written informed consent from each subject, or the legally designated representative of a vulnerable subject, is obtained prior to the initiation of any study-related procedures. As per ISO 14155:2020, vulnerable subjects are defined as individuals who are unable to fully understand all aspects of the investigation that are relevant to the decision to participate, or who could be manipulated or unduly influenced as a result of a compromised position, expectation of benefits, or fear of retaliatory response.

Inclusion of vulnerable subjects in this clinical study is considered ethical given that this is a post-market clinical investigation without additional invasive or burdensome procedures.

The Investigator must comply with the requirements specified in protocol **Section 7.3**.

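### The protocol says no invasive procedure is added, yet the IVUS Sub-study requires intravascular imaging, and its baseline run normally falls before adverse event collection begins

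*Combined protocol and SAP*

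**What the plan says.** **Burden and risk.** Section 6.5 classes the study as non-interventional and states: "No additional invasive or burdensome diagnostic or monitoring procedures are applied to the subjects". Section 8.3 says: "All assessments (with the exception of questionnaires) are considered to be standard of care". The tests it then names are all non-invasive, IVUS is not among them, and it sends the reader to the device instructions for procedural risks. Section 11.2 calls the inclusion of vulnerable subjects ethical because this is a "post-market clinical investigation without additional invasive or burdensome procedures".

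**The sub-study.** Section 6.9 says: "Up to 50 subjects will be enrolled in an optional IVUS Sub-study". Footnote 3 of Table 1 sets the schedule: "For the IVUS Sub-study, IVUS imaging is required at baseline, immediately post-IVL, and end of procedure". The synopsis (Section 2.0), Section 7.7.1 and Section 7.7.11 repeat the requirement. Sections 6.9, 7.7.1 and 7.7.11 also refer to a separate IVUS protocol, which is not among the supplied documents.

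**Start of safety collection.** Section 10.4.1 says: "All AE information will be collected from enrollment through 24 months follow-up". Section 10.4.2 gives the same start for serious events. Sections 7.2 and 7.7.5 place enrollment at the point when all eligibility criteria are met and the IVL catheter has gone in over the guidewire. Under Section 7.2, a subject who fails angiographic eligibility is documented in the data capture system as a screen failure.

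**The concern.** Two things are at odds. First, the burden statements are untrue of the sub-study. Some sites may use IVUS routinely, but a sub-study subject must have all three runs whatever the local practice. An ethics committee reading Sections 6.5, 8.3 and 11.2 is told that nothing invasive is added. It is asked to accept vulnerable subjects on that basis, including those for whom a representative consents under Section 7.3.2.

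Second, the safety window opens at IVL catheter insertion, while the first required IVUS run is a pre-treatment image. A consented person could be harmed by a study-required invasive step and then not be enrolled. Nothing in the supplied text would require the event to be recorded. At stake are the completeness of the sub-study's safety record and the accuracy of what committees and subjects are told.

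**Working it through.** The plan gives no figure on this point, so there is none to reproduce. The check is one of sequence, followed by arithmetic for scale.

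**Sequence**

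1. Consent. Section 7.3 requires it before any study-specific procedure, so anyone having a study-required baseline IVUS run has already consented.
2. Baseline IVUS. Table 1 contrasts this run with the one after lithotripsy, so it images the untreated lesion. Criterion 12b (Section 7.2.1) and Section 7.7.2 also let IVUS establish the calcium requirement.
3. Enrollment. Section 7.7.5 requires every eligibility criterion to be met and the IVL catheter to be inserted. A run that settles criterion 12b must therefore precede enrollment. Otherwise the order is not stated. Before is the natural reading, but exceptions are possible, for example a failed first IVL crossing followed by pre-dilatation.
4. AE and SAE collection. It starts at step 3 (Sections 10.4.1 and 10.4.2), so the baseline run normally falls between consent and the opening of the window.

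**What happens to an injury in that interval**

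- *Subject not enrolled afterwards.* Section 7.2 requires a screen-failure record. No supplied section requires an AE record. This route needs no special reading of the exclusion criteria: a subject whose IVUS shows too little calcium, and who qualifies by neither of the other two routes in criterion 12, is enough.
- *Subject enrolled afterwards.* Table 1 ticks both IVUS and Adverse Events in its column for enrollment and procedure, which suggests the event could be recorded. Section 10.4 starts collection at enrollment, which suggests it need not be. The text is unclear.

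**Scale**

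Inputs: up to 50 sub-study subjects (Section 6.9), up to 250 in total (Section 9.3), three timepoints (Table 1).

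- Share of subjects: 50/250 = 20%.
- IVUS timepoints with one imaged lesion per subject: 50 × 3 = 150, of which 50 are baseline.

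The documents give no IVUS complication rate, so r below is an assumption. The chance of at least one event in 50 baseline runs is 1 − (1 − r)^50, and the expected number is 50r.

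| Assumed r per run | Chance of ≥1 event | Expected events |
|---|---|---|
| 0.5% | 1 − 0.995^50 = 22.2% | 0.25 |
| 1% | 1 − 0.99^50 = 39.5% | 0.5 |
| 2% | 1 − 0.98^50 = 63.6% | 1.0 |
| 5% | 1 − 0.95^50 = 92.3% | 2.5 |

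These are chances that an event occurs, not that it goes unreported. Only events in subjects then not enrolled certainly fall outside the required data, and the documents give no basis for that fraction. If no events were recorded in 50 runs, the exact two-sided 95% upper limit would still be 1 − 0.025^(1/50) = 7.1%, so a few missed events would matter to any safety statement about the imaging.

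**The case against.** The strongest reply is that much of this is already handled, or may be handled in documents not supplied.

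- **Table 1 and the AE definition.** Table 1 puts IVUS and Adverse Events in one column. Section 10.1.1 counts procedure-related events as AEs, and Section 10.2 asks for a procedure relationship. This stands for subjects who go on to be enrolled: a site could well record the event. It does not reach subjects who are never enrolled.
- **Separate documents.** The IVUS protocol, the core-lab angiographic protocol and the consent form could set safety reporting or the order of imaging. This stands, and it is why the point is that harm can go unreported, not that it will. None of those documents would correct Sections 6.5, 8.3 or 11.2.
- **Optional sub-study.** Participation is optional, and the documents do not say whether vulnerable subjects enter it. That is true, but no section exempts the sub-study from the burden claim or limits who may join.

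Stronger readings are tempting, and the documents do not carry them:

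- *A baseline IVUS injury triggers exclusion 28.* That criterion is worded around guidewire crossing. An IVUS injury after a successful crossing is not named, so screening out by this route is only one possible reading.
- *Screened-out injuries inflate Procedure Success.* That endpoint is analysed in enrolled subjects (Section 9.4). An injury before any IVL catheter is inserted lies outside that population.
- *An injury from the last run escapes the graded angiogram.* Section 7.7.1 does not give the order of the final cine and final IVUS run, but silence does not show that IVUS comes last. Such an injury would also fall inside the AE window.
- *There could be 300 runs.* That needs two lesions in all 50 subjects and imaging of each; the documents set IVUS by timepoint, not by lesion.

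**Conclusion.** The point holds as a contradiction in the text together with a narrow gap in safety capture. Sections 6.5 and 11.2 deny an invasive addition that the sub-study requires in up to 20% of subjects, and Section 8.3 leaves it out of the stated risks. Harm from the baseline IVUS run in a consented subject who is then not enrolled has no required reporting route in the supplied text; for later-enrolled subjects the text is unclear.

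The size is at most 50 baseline and 150 total IVUS timepoints, counting one imaged lesion for each of 50 sub-study subjects. The number of missed events cannot be estimated, because neither the complication rate nor the share of subjects stopping after the baseline run is given.

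The conclusion assumes that the baseline run usually precedes IVL catheter insertion, which is certain only when it serves criterion 12b, and that the separate IVUS protocol does not already close the gap. A reader might infer that the primary effectiveness endpoint is biased in the device's favour. The documents do not show that.

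**What to change.** 1. In Sections 10.4.1 and 10.4.2, start AE and SAE collection for consented sub-study subjects at the first study-required IVUS run, and require reporting for those who then do not reach enrollment. Align Table 1 with this. If the IVUS protocol already provides for it, cross-refer to it.
2. Reconcile Sections 6.5, 8.3 and 11.2 with the sub-study: state that it adds an invasive procedure, list the risk, and justify separately any inclusion of vulnerable subjects in it.
3. As an inexpensive safeguard, state in Sections 7.7.1 and 7.7.11 that the final core-lab cine is acquired after the last IVUS run, unless the core-lab protocol already says so.

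The cost is protocol and consent wording, plus AE forms for the few sub-study subjects who stop before enrollment. No procedure is added, and the sample size and endpoint definitions do not change. The small downside is a few more reported events.

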## 6.6 Site Selection

Up to 40 global sites will participate in the study.

## 6.7 Number of Subjects

Up to 250 subjects with moderate to severe calcified peripheral artery disease below the knee presenting with Rutherford Category (RC) 3 to 5 will be enrolled. The RC 3 will be capped at 20% of total enrollment. If a subject has a target lesion in each limb and one of the limbs is RC 3, this subject will count toward the Rutherford Category 3 cap. Up to two (2) target lesions allowed for each subject. Each site will be allowed to enroll up to 15% (37 subjects) of total study enrollment.

## 6.8 Clinical Study Duration

Enrollment is anticipated to last approximately 24 months. Study subjects will be followed through hospital discharge, 30 days, and 6-, 12-, and 24-months post-procedure. Duplex ultrasound (DUS) assessments will be completed at 6 and 12 months. Total anticipated study duration is 48 months.

## 6.9 IVUS Sub-study

Up to 50 subjects will be enrolled in an optional IVUS Sub-study. All study centers with intravascular ultrasound (IVUS) imaging capability will have the opportunity to participate in the Sub-study. A separate IVUS protocol will be provided to participating study centers.

	No.: CP 65007	REV. C
	TITLE: Disrupt PAD BTK II Study	
	CLASS: CLINICAL PROTOCOL	PAGE 23 OF 71

## 7.0 STUDY PROCEDURES

---

### 7.1 Screening

Patients presenting to the institution with known infrapopliteal disease requiring an interventional procedure will be evaluated for eligibility and participation in the clinical study. A member of the participating site's study team will perform an initial evaluation of the potential participant's medical history and previously performed examinations to assess for initial eligibility. Pre-procedure imaging (DUS, angiogram, CTA, MRA) should be performed according to the institution's standard of care.

Potential subjects will be screened for eligibility. Written informed consent will be obtained prior to any study-specific requirements. A potential subject will be informed of the elements of the clinical study including risks, potential benefits, and required follow-up procedures prior to obtaining the potential subject's informed consent.

### 7.2 Subject Selection

Subjects who meet the clinical inclusion/exclusion criteria will undergo an angiogram performed according to the institution's standard of care. If all angiographic eligibility criteria are met, the subject is considered to be enrolled once the peripheral IVL catheter has been inserted over a 0.014" guidewire that crossed the target lesion. A subject is considered an angiographic screen failure if they do not meet angiographic eligibility criteria. Subjects who screen fail will be documented as such in the electronic data capture (EDC) system.

#### 7.2.1 Inclusion Criteria

Subjects are required to meet all of the following inclusion criteria in order to be enrolled in the clinical study. For lesion characteristics, each target lesion must meet eligibility. The subject would, at the investigator's discretion, receive the treatment required per Study Protocol which also may be per standard of care (SOC).

##### General Inclusion Criteria

1. Age of subject is  $\geq 18$ .
2. Subject is able and willing to comply with all assessments in the study.
3. Subject or subject's legal representative has been informed of the nature of the study, agrees to participate, and has signed the approved consent form.
4. Rutherford Category 3, 4, or 5 in the target limb.
5. Estimated life expectancy  $>1$  year.

##### Angiographic Inclusion Criteria

6. Up to 2 below-the-knee target lesion(s) in native vessels in one or both limbs.
7. Target lesion from the distal segment (P3) of the popliteal artery to the ankle joint.

	No.: CP 65007	REV. C
	TITLE: Disrupt PAD BTK II Study	
	CLASS: CLINICAL PROTOCOL	PAGE 24 OF 71

8. Target lesion reference vessel diameter (RVD) between 2.0mm and 4.0mm by investigator visual estimate.
9. Target lesion with  $\geq 70\%$  stenosis by investigator visual estimate.
10. Target lesion length is  $\leq 200\text{mm}$  by investigator visual estimate. Target lesion can be all or part of the 200mm treated zone.
11. Distal reconstitution of at least one pedal vessel ( $<50\%$  stenosis) (desert foot excluded) in the target limb.
12. Evidence of at least moderate calcification at the target lesion site by angiography/IVUS OR non-dilatable lesion indicating presence of calcium. Must meet one of the following:
  - a. Angiography requires fluoroscopic evidence of calcification on parallel sides of the vessel and extending  $>50\%$  the length of the lesion.:
  - b. IVUS requires presence of  $\geq 270$  degrees of calcium over the course of at least 10mm.
  - c. Non-dilatable lesion requires attempted treatment with PTA during the index procedure with residual stenosis  $>50\%$  and no serious angiographic complications.

### 7.2.2 Exclusion Criteria

Subjects who meet any of the following exclusion criteria may not be enrolled in the study:

#### General Exclusion Criteria

1. Rutherford Clinical Category 0, 1, 2, and 6 (target limb).
2. Subjects with osteomyelitis or deep soft tissue infection are excluded unless infection can be treated with an individual toe ray amputation or transmetatarsal amputation (TMA) in the target limb in the opinion of the investigator.
3. History of endovascular or surgical procedure on the target limb within the last 30 days, or planned within 30 days of the index procedure with the exception of toe amputation(s).
4. Subject in whom antiplatelet or anticoagulant therapy is contraindicated.
5. Subject has known allergy to contrast agents or medications used to perform endovascular intervention that cannot be adequately pre-treated.
6. Subject has known allergy to urethane, nylon, or silicone.
7. Myocardial infarction within 30 days prior to enrollment.
8. History of stroke within 60 days prior to enrollment.

	No.: CP 65007	REV. C
	TITLE: Disrupt PAD BTK II Study	
	CLASS: CLINICAL PROTOCOL	PAGE 25 OF 71

9. Subject has acute or chronic renal disease with eGFR <30 ml/min/1.73m^2 (using CKD-EPI formula), unless on renal replacement therapy.
10. Subject is pregnant or nursing.
11. Subject is participating in another research study involving an investigational agent (pharmaceutical, biologic, or medical device) that has not reached the primary endpoint.
12. Subject has other medical, social or psychological problems that, in the opinion of the investigator, preclude them from receiving this treatment, and the procedures and evaluations pre- and post-treatment.
13. Covid-19 diagnosis within 30 days.
14. The planned use of cutting/scoring balloons, re-entry or atherectomy devices in target lesions during the index procedure.
15. Planned major amputation (of either leg).
16. Acute limb ischemia (of either leg).
17. Occlusion of all the inframalleolar outflow arteries/vessels (i.e., desert foot) in the target limb.
18. Subject has an anticipated life span of less than one (1) year.
19. Subject already enrolled into this study.

